15.5. Liability

Medicine is not an exact science and no guarantees can be made as to the results. The procedure to be followed in this study may involve risks and discomforts, as with any procedure. All the risks of being treated with the Barrx™ Flex Radiofrequency Ablation System are the same whether in clinical trials or not. Nevertheless, study related insurance will be available.

The sponsor shall be responsible for any medical expense and will provide compensation for injury or death resulting from participation in the study. However, it shall be excluded from the sponsor's responsibility if the injury or death is in a result of medical institute or the investigator's fault.

In the event of physical injury or physical illness resulting from participation in this study, any medical treatment that is needed will be provided. The expense of any relevant medical treatment for physical injury or physical illness resulting from participation in this study will be reimbursed by Medtronic.

15.6. CIP Amendments

Changes or clarifications to the protocol may be described in a formal protocol amendment as needed, including a summary of changes and a rationale for the changes. Changes to the CIP will not be implemented until all necessary approvals/favorable opinions are obtained from the appropriate IRB/ECs or regulatory authority, as appropriate.

15.7. Record Retention

The investigator will maintain the records of the study including all pertinent correspondence, the study protocol with any/all amendments, all correspondence with and approval from the IEC, the clinical trial

agreement, the Investigator Agreement, device accountability records, individual subject records, and signed ICFs. Subject files and other source data must be kept for a period of not less than 2 years after the latter of the following two dates: the date on which this investigation is terminated or completed, or the date that the records are no longer required for purposes of supporting a premarket application. Records may need to be maintained by the Principal Investigator for a longer duration if national regulations require or if agreed to in writing with the Sponsor. All data and documents should be made available if requested by relevant authorities. The sponsor must keep study records for no less than 15 years.

15.8. Publication and Use of Information

The Medtronic Publication and Authorship Policy is aligned with the International Committee of Medical Journal Editors (ICMJE) recommendations (www.icmje.org). The Sponsor will seek to publish, in appropriate peer-reviewed journals and scientific conferences, results of clinical studies where human subjects are involved, regardless of outcome. While study results are owned by the Sponsor, all data on which a publication is based will be made available to all authors as required for their participation in the publication process. Furthermore, data may be published or used by study investigators provided that such publication or use is in accordance with this protocol, the Medtronic Publication and Authorship Policy, and the Clinical Investigation Agreement. Investigators must submit a copy of all manuscripts and/or abstracts to the Sponsor for review and comment 30 days prior to planned submission. Medtronic acknowledges that its right to review and comment shall relate solely to the proprietary, licensing, and/or confidential rights Medtronic may have in such proposed publication, rather than whether such results and/or opinions are favorable to Medtronic.

The publication of substudies, post-hoc analyses, regional results, or single-center experiences based on multicenter clinical studies should not precede that of the primary multicenter publication, and should cite the primary publication whenever possible, as required by specific journal and scientific meeting guidelines.

Medtronic involvement in a publication (e.g., funding of the study; sponsor of the study; collection, analysis, and interpretation of data; professional writing assistance) must be disclosed according to journal-specific policies, submission requirements, and prevailing editorial standards, in addition to those specified by International Committee of Medical Journal Editors. Authors must ensure that an acknowledgement/disclosure statement is included in the body of the manuscript for Medtronic to review for accuracy. All authors must also disclose financial or personal affiliations that could be considered conflicts of interest as per journal/conference requirements.

To enable health care providers, payers, and patients access to the wealth of Medtronic's research, Medtronic will report its scientific data in accordance with the principles outlined in the Guidance Document on Registration and Reporting Results of Company-Sponsored Clinical Trials Under FDAAA 2007 (Title VIII).

6.0	
 • Exclusion criteria # 6 revised to exclude patients who have had EMR or ESD <3 months prior. • Inclusion criteria #9 revised to include "EMR or ESD occurred > 3 months before enrollment, patients may be eligible for the study if procedure was curative (negative margins and no risk of lymph node involvement) and the patient has no other findings concerning for cancer." • Included 5 satellite sites of CICAMS • Run-in patients defined as up to 5 patients for each endoscopist that is inexperienced with RFA or has had no RFA onsite training from CICAMS. 	
██████████ Director, Global Clinical Affairs

7.0	
 • Remove reference to 5 satellite sites of CICAMS 	
██████████ Director, Global Clinical Affairs
 
██████████ Clinical Research Specialist

RFA	radiofrequency ablation
SAE	serious adverse event
SADE	serious adverse device effect
SCCA	squamous cell carcinoma
TA	treated area
USADE	unanticipated serious adverse device effect
USL	unstained lesion
VAS	visual analog scale
WLE	white light endoscopy

This document is electronically controlled. Printed copies are considered uncontrolled.

Confidential

12JUL2017

3. Introduction

The REACH study is a multicenter, prospective cohort clinical study to assess (i) the effectiveness of radiofrequency ablation (RFA) using the Barrx™ Flex Radiofrequency Ablation System in the eradication of diseased epithelium at 12 months post-treatment, and (ii) the durability of established eradication of disease during 5 years of follow-up, in subjects with early ESCN, defined as MGIN or HGIN.

This statistical analysis plan (SAP) provides a detailed description of the statistical methods and procedures to be implemented during the analysis of the REACH study. The document is intended to support the generation of a Clinical Study Report (CSR) for the Clinical Investigational Plan (CIP) v4 , dated July 03, 2017.

4. Study Objectives

4.1. Primary Objective(s)

The primary objective is to measure the effectiveness of the Barrx™ Flex Radiofrequency Ablation System in the eradication of diseased epithelium at 12 months post-treatment in subjects with macroscopically flat-type – defined as Paris type 0-IIb on white light endoscopy (WLE) and Lugol’s endoscopy- early esophageal squamous cell neoplasia (ESCN), defined as moderate-grade squamous intraepithelial neoplasia (MGIN) or high-grade squamous intraepithelial neoplasia (HGIN).

4.2. Secondary Objective(s)

The secondary objectives are to assess safety, to measure durability of complete response during long-term follow-up, and to measure overall ESCC progression and associated mortality after treatment.

5. Investigation Plan

This multicenter, prospective cohort clinical study will evaluate a subject population having macroscopically flat type (type 0-IIb) esophageal lesions with histological evidence of MGIN or HGIN in biopsy specimens obtained from the esophagus.

For patients who meet all of the inclusion criteria and none of the exclusion criteria, step-wise endoscopic RFA will be performed in 3 month intervals per the Patient Flow Diagram (Figure 1). Each decision point in the flow diagram regarding endoscopy, staining, RFA, biopsy, and patient advancement to subsequent study visits is fully delineated in the diagram. The study primary endpoint biopsies are obtained at 12 months from the initial treatment.

Subject’s duration of involvement in the study is expected to be up to 60 months (estimated based on primary RFA plus 12 months of treatment phase and 48 months of follow-up). The overall study is expected to last a total of 6 years if enrollment is completed in a timely manner.

This document is electronically controlled. Printed copies are considered uncontrolled.

Confidential

12JUL2017

Patients with a CR at 12 months will enter the follow-up phase as described in figure 2 and section 9.4.2 of the CIP..

Patients with residual ESCN at 12 months will be defined as treatment failures, and will undergo escape treatment within 3 months (+/- 4 weeks). If CR will be re-established after escape treatment, patients will stay in the trial and will be followed-up and treated if necessary, according to figure 2 of the CIP. If non-endoscopic treatment is performed at 12 months, or if pathology indicates non-endoscopic treatment, patients won't be treated and/or followed-up according to the study protocol, but will still be followed-up until 5 years after baseline to assess secondary endpoints.

This document is electronically controlled. Printed copies are considered uncontrolled.

Confidential

12JUL2017

[figure not shown]

Figure 1. Decision Tree for Subject Flow through Treatment (adapted from He et al., 2014)

This document is electronically controlled. Printed copies are considered uncontrolled.

Confidential

12JUL2017

6. Determination of Sample Size

The proposed sample size of 100 subjects is considered adequate for the study objective. From published data, a complete response rate of 80%-90% of the RFA treatment is expected at 12 months post-treatment for the subject population (He et al., 2015). With 100 study subjects, a precision (half 95% CI width) of 6%-8% will be achieved for estimating the primary endpoint of complete response rate. For safety, a sample of 100 subjects will have greater than a 99% chance to detect a rare event of 5% incidence or an 85% chance to detect a rare event of 2% incidence. The NIH defines an acceptable dropout rate at 20% or less. However, over 70% of all high-quality clinical studies in China had a dropout rate lower than 10%. For example, the dropout rate at CICAMS was 3% in a previous ESCN study.

7. Statistical Methods

7.1. Study Subjects

7.1.1. Disposition of Subjects

Subject disposition (e.g., number completing the study, number lost-to-follow-up) will be summarized with frequency tables.

7.1.2. Clinical Investigation Plan (CIP) Deviations

A CIP deviation is defined as an event where the Investigator or study personnel did not conduct the study according to the CIP. Deviations shall be reported regardless of whether medically justifiable or taken to protect the subject in an emergency.

The total number of protocol deviations and total number of subjects with deviations will be provided by deviation type for all enrolled subjects. Number of protocol deviations and number of subjects with deviations by each investigational site will also be provided.

7.1.3. Analysis Sets

The primary analysis will be based on a per-protocol basis. Subjects who enrolled into the study (a patient is defined as enrolled after introduction of RFA catheter at primary RFA), and had valid study outcomes with no major protocol violations will be included in the analysis. Only the 100 cohort patients will be included for primary analysis.

Additional analyses based on subsets of the study subjects or combining run-in subjects may be performed to provide further support to the study results.

All enrolled study subjects will be included in the safety analysis.

This document is electronically controlled. Printed copies are considered uncontrolled.

Confidential

12JUL2017

7.2. General Methodology

In general, descriptive statistics will be used to summarize study outcomes. For continuous variables, the number of available observations, mean, standard deviation, median, minimum and maximum values will be provided. For categorical variables, frequency and percentage will be used. Unless otherwise specified, statistical assessments will be based on two-sided tests at an alpha level of 0.05, which include Student-t or Wilcoxon rank-sum test for continuous variables, and Chi-square or Fisher's exact test for categorical variables. Other statistical methods may be used as appropriate. Statistical analysis will be performed using SAS Version 9.2 or higher (SAS Institute Inc., Cary, NC) or other valid statistical software.

7.3. Center Pooling

This is a multi-center clinical study, with standardization of subject enrollment, data entry and adverse event reporting. All investigational sites will follow the requirements of a common protocol, data collection procedures and forms. All the data will be pooled for reporting.

7.4. Handling of Missing Data and Dropouts

The number and proportion of subjects eligible for and compliant with each follow-up examination will be presented. Subjects who withdraw from the study will be tabulated with reasons for withdrawal. Sensitivity analysis for discontinuations or missing data will be conducted to assess the robustness of study results which may include last observation carried forward, multiple imputations, and tipping point analysis, as appropriate.

7.5. Adjustments for Multiple Comparisons

Considering the feasibility nature of the study, no multiplicity adjustment is considered.

7.6. Demographic and Other Baseline Characteristics

The demographic, baseline characteristics, patient history, BQE and pathology will be summarized. Discrete variables will be presented using frequency distributions and cross tabulations. For continuous variables, statistics will include the number of observations, mean, standard deviation, median, minimum, and maximum.

7.7. Treatment Characteristics

The procedure characteristics, including primary RFA and additional RFA as well as the endoscopy information will be summarized using descriptive statistics for continuous variables (mean, standard deviation, number of observations, median, minimum and maximum) and frequency tables for discrete variables.

This document is electronically controlled. Printed copies are considered uncontrolled.

Confidential

12JUL2017

7.8. Interim Analyses

Efficacy and safety will be specifically assessed after enrollment of 25 and 50 patients. Additional interim data analyses may be performed, as needed, for requirements related to abstract submission, IRB requests, or DSMB requests.

7.9. Evaluation of Objectives

The primary effectiveness will be measured as the percentage of subjects with complete response within the treatment area. The response rates and 95% confidence intervals will be summarized. Run-in subjects, defined as the first 5 subjects enrolled per endoscopist, will be summarized separately.

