Sample Size	Up to 100 subjects will be included in the cohort, in up to 10 clinical sites. This is excluding up to 50 “run-in” subjects, defined as up to 5 patients for each endoscopist that is inexperienced with RFA or has had no onsite RFA training from CICAMS. Data from the run-in patients will be analyzed separately from the cohort.
Inclusion/Exclusion Criteria	Inclusion Criteria

Medtronic Confidential

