5.2. Endpoints

5.2.1. Primary Endpoint

The percentage of subjects with “complete response (CR),” defined as complete eradication of squamous histological abnormalities (MGIN or worse) within the treatment area (TA) at 12 months after the initial treatment session (per protocol analysis). Patients who show ESCC in biopsies or resection samples are defined as failures for this endpoint, even if subsequent biopsies at 12 months indicate CR. The primary study hypothesis is that 80% of treated subjects will have a complete response.

Patients

All 100 patients who are included in the cohort will be assessed for the primary endpoint. The run-in patients will not be included for the primary endpoint analysis.

Biopsies

Only biopsies obtained from the original USL bearing portion of the esophagus (the treatment area) will be used in the analysis for the primary endpoint analysis. MGIN or worse noted in any biopsy from outside this region are not considered failures of ablation for the purposes of the primary endpoints.

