5.2.2. Secondary Endpoint(s)

1. The percentage of subjects with a sustained CR during long-term follow-up, defined as patients with a CR at 12 months that sustained this absence of squamous abnormalities (MGIN or worse) during all subsequent FU endoscopies through 60 months.
2. Proportion of patients with CR after primary RFA, defined as absence of MGIN or worse in any of the biopsies from the treatment area, at the three month visit.
3. Proportion of patients demonstrating progression within the treatment area (TA), defined as detection of ESCC in biopsy or resection specimen at any time within the first 12 months.
4. Occurrence of serious adverse device effects (SADE) after RFA treatment.
5. Proportions of “run-in” subjects, are defined as the first 5 subjects enrolled per endoscopist that is inexperienced with RFA or has had no RFA onsite training from CICAMS, with a CR at 3 and 12 months after the initial treatment session, and with sustained CR during follow-up.
6. Proportion of patients with CR at 12 months who subsequently developed recurrent disease in TA, defined as MGIN or HGIN for patients with MGIN at baseline, and MGIN or HGIN for patients with HGIN at baseline.
7. Proportion of patients with CR at 12 months who subsequently developed progressive disease in TA, defined as ESCC in biopsy or resection specimen.
8. Durability after reiterative RFA, defined as proportion of patients with a CR at 12 months who sustain or re-establish CR upon reiterative RFA treatment sessions during FU.
9. Durability after additional endoscopic treatment, defined as proportion of patients with CR at 12 months who sustain or re-establish CR upon endoscopic treatment (RFA and eventually in combination with EMR or ESD) during FU.
10. Esophageal squamous cell cancer mortality.
11. Proportion of patients demonstrating MGIN or worse outside the TA during treatment phase or follow-up.

6. Study Design

This clinical study will evaluate a subject population having macroscopically flat type (type 0-IIb) esophageal lesions with histological evidence of MGIN or HGIN in biopsy specimens obtained from the esophagus.

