7.9.1. Primary Endpoint

The primary endpoint is the percentage of subjects with "complete response (CR)", defined as complete eradication of squamous histological abnormalities (MGIN or worse) within the treatment area (TA) at 12 months after the initial treatment session (per-protocol analysis). Patients who show ESCC in biopsies or resection samples are defined as failures for this endpoint, even if subsequent biopsies at 12 months indicate CR.

The primary study hypothesis is that 80% of treated subjects will have a complete response.

Patients

All 100 patients that are included in the cohort will be assessed for the primary endpoint. The run-in patients will not be included for the primary endpoint analyses.

Biopsies

Only biopsies obtained from the original USL bearing portion of the esophagus (the treatment area) will be used in the analysis for the primary endpoint at 12 months. At 12 months, MGIN or worse noted in any biopsy from outside this region are not considered failures of ablation for the purposes of the primary endpoint.

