7.9.2. Secondary Endpoint(s)

1. The percentage of subjects with a sustained CR during long-term follow-up, defined as patients with a CR at 12 months that sustained this absence of squamous abnormalities (MGIN or worse) during all subsequent FU endoscopies through 60 months.
2. Proportion of patients with CR after primary RFA, defined as absence of MGIN or worse in any of the biopsies from the treatment area, at the three month visit.
3. Proportion of patients demonstrating progression within the treatment area (TA), defined as detection of ESCC in biopsy or resection specimen at any time within the first 12 months.
4. Occurrence of serious adverse device effects (SADE) after RFA treatment.
5. Proportions of "run-in" subjects, defined as the first 5 subjects enrolled per endoscopist, with a CR at 3 and 12 months after the initial treatment session, and with sustained CR during follow-up.

This document is electronically controlled. Printed copies are considered uncontrolled.

Confidential

12JUL2017

6. Proportion of patients with CR at 12 months who subsequently developed recurrent disease in TA, defined as MGIN or HGIN for patients with MGIN at baseline, and MGIN or HGIN for patients with HGIN at baseline.
7. Proportion of patients with CR at 12 months who subsequently developed progressive disease in TA, defined as ESCC in biopsy or resection specimen.
8. Durability after reiterative RFA, defined as proportion of patients with a CR at 12 months who sustain or re-establish CR upon reiterative RFA treatment sessions during FU.
9. Durability after additional endoscopic treatment, defined as proportion of patients with CR at 12 months who sustain or re-establish CR upon endoscopic treatment (RFA and eventually in combination with EMR or ESD) during FU.
10. Esophageal squamous cell cancer mortality.
11. Proportion of patients demonstrating MGIN or worse outside the TA during treatment phase or follow-up.

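### The SAP counts every endoscopist's first five subjects as run-in; protocol v7.0 counts only those of RFA-inexperienced or untrained endoscopists, so the primary analysis set is not uniquely defined

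*SAP*

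**What the plan says.** SAP 7.9: "Run-in subjects, defined as the first 5 subjects enrolled per endoscopist, will be summarized separately". SAP 7.9.2 item 5 repeats this for the run-in endpoint: "defined as the first 5 subjects enrolled per endoscopist, with a CR at 3 and 12 months". Neither place attaches a condition on the endoscopist's experience or training. SAP section 3 says the plan supports "Clinical Investigational Plan (CIP) v4", dated 3 July 2017; the SAP itself is dated 12 July 2017.

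The protocol supplied is version 7.0 of 15 March 2018. Its synopsis sets a cohort of up to 100 and counts the run-in group, at most 50, on top of it. It gives the membership rule for that group as follows: "defined as up to 5 patients for each endoscopist that is inexperienced with RFA or has had no onsite RFA training from CICAMS". Section 8.2 gives the same restriction, and 5.2.2 item 5 says that they "are defined as the first 5 subjects enrolled per endoscopist that is inexperienced with RFA or has had no RFA onsite training from CICAMS".

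The two documents agree on what follows from run-in status. Protocol 5.2.1: "The run-in patients will not be included for the primary endpoint analysis". SAP 7.9.1: "The run-in patients will not be included for the primary endpoint analyses".

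**The concern.** Run-in status decides whether a patient counts in the primary endpoint. If the two documents define run-in differently, they can define different primary sets.

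The patients affected are the first five of any endoscopist who is both experienced with RFA and trained onsite by CICAMS. Under the protocol they belong to the primary cohort. Under the SAP they are run-in, are excluded from the primary analysis and enter secondary endpoint 5.

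Two things are at stake. First, the study is single-arm and non-blinded, so a choice between two written rules could be made after responses are known. Second, endpoint 5 under the protocol describes results from inexperienced or untrained operators. Under the SAP rule it would also include patients of experienced, trained operators and would no longer answer that question.

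**Working it through.** **The plan's own precision.** SAP section 6 and protocol 13.2 expect a complete response rate of 80%-90% and state a 95% half-width of 6%-8% with 100 subjects. Using 1.96 × √(p(1−p)/n):

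- p = 0.80, n = 100: 1.96 × √(0.16/100) = 7.84 points
- p = 0.90, n = 100: 1.96 × √(0.09/100) = 5.88 points

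The stated 6%-8% is reproduced.

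**Which patients change sets.** Let k be the number of endoscopists who are both experienced and CICAMS-trained, each enrolling at least five subjects. Neither document gives k. If 100 cohort patients are enrolled under the protocol rule and then sorted by the SAP rule, the primary set is 100 − 5k.

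| k (assumed) | Primary n | Half-width at 80% | Half-width at 90% |
|---|---|---|---|
| 0 | 100 | 7.84 | 5.88 |
| 1 | 95 | 8.04 | 6.03 |
| 2 | 90 | 8.26 | 6.20 |
| 5 | 75 | 9.05 | 6.79 |
| 10 | 50 | 11.09 | 8.32 |

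At k = 1 or 2 every value still rounds to 6% or 8%. The last two rows only show how the effect grows; nothing in the documents supports k that large.

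**Shift in the estimate.** Assume the moved patients' response rate differs from the overall rate by 10 points. The estimate then moves by 10 × 5/95 = 0.53 points at k = 1 and by 10 × 10/90 = 1.11 points at k = 2.

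**Endpoint 5.** Assume the protocol rule yields the full 50 run-in subjects. The SAP rule then yields 55 at k = 1, of whom 5/55 = 9% come from endoscopists with no run-in under the protocol. At k = 2 it yields 60, of whom 10/60 = 17% do.

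**The run-in cap.** Protocol 8.2 allows at most 10 sites with one or two endoscopists each, so up to 20 endoscopists, and at most 50 run-in patients. If each endoscopist enrols at least five, the SAP rule gives 5 × 10 = 50 run-in subjects with 10 endoscopists and 5 × 20 = 100 with 20. Above 10 such endoscopists the SAP rule exceeds the protocol's cap. This does not establish k.

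**The case against.** The strongest reply is that this is version lag rather than two competing rules. The SAP was written for protocol v4, and protocol 13.6 says departures from the planned methods will be explained in the SAP. The SAP declares none here, so the protocol should stand. The SAP also ties the primary analysis to the 100 cohort patients (7.1.3, 7.9.1), and the fall to 95 or 90 requires enrolling under one rule and sorting under the other. Under either rule, run-in status depends on the endoscopist and the order of enrolment, not on outcome. No success threshold is set on the confidence interval, so a shift of about one point would reverse no decision.

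Much of this is fair. It explains how the mismatch probably arose, and the numerical effect at small k is minor. The protocol's version history lists the restricted definition under v6.0, which fits that explanation, but the conflict rests on the current texts alone. Only one SAP version was supplied, so a later one cannot be ruled out.

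The reply does not remove the conflict. Protocol 13.6 sets no order of precedence, and an SAP dated July 2017 could not have declared a departure from a March 2018 text. Reference to the 100 cohort patients does not help, because membership of that cohort depends on the disputed definition. The SAP is consistent with itself; it disagrees with the current protocol. The optional analyses that add run-in subjects (protocol 13.3, SAP 7.1.3) do not say who is in the primary set either.

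**Conclusion.** The concern holds. As written, the SAP and protocol v7.0 can give different primary sets and different run-in groups for endpoint 5, and neither says which definition governs.

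The textual conflict is certain; its numerical size is not known. It is nil if no endoscopist is both experienced and CICAMS-trained. With one or two such endoscopists (assumed), it costs at most about 0.4 points of half-width. It moves the estimate by about 0.5 or 1.1 points if a 10-point difference in response is also assumed. An effect on the trial's conclusion is not shown. The point should be fixed because membership of the primary set ought to follow from one rule, settled without sight of outcomes.

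**What to change.** - In SAP 7.9 and 7.9.2 item 5, replace the run-in definition with that of protocol v7.0. Word it as the first subjects enrolled, to a maximum of five, for each endoscopist who is inexperienced with RFA or has no onsite CICAMS training. This also settles the small difference between the maximum of five in the synopsis and 8.2 and the first five in 5.2.2 item 5.
- Change the protocol reference in SAP section 3 from v4 to v7.0.
- In SAP 7.1.3, state that the primary set uses run-in status fixed in a dated list, by endoscopist and subject, before outcome data are reviewed. The list should show how any subjects enrolled under earlier protocol versions are classified.

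The cost is one short SAP revision and one list. No new data are needed.
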